An increasing number of schools in rural settings are employing the multi-tier positive behavioral interventions and supports (PBIS) framework to improve school-climate. PBIS can also be used as a framework for the adoption and integration of evidence-based practices (EBPs) for children's mental health concerns. A key challenge is that school personnel need technical assistance (training plus ongoing consultation) in order to implement EBPs with fidelity. In urban and suburban schools, this support can be provided to school staff on site. However, providing ongoing on-site support is not feasible or sustainable in the majority of rural schools, due to their remote physical location. For this reason, video technology has been recommended for the training of behavioral health staff (BHS) in under-served rural communities.

Objectives:

The purpose of this study is to test the effectiveness of a remote training platform with BHS in schools serving rural communities.

Study Design:

This study is a pilot randomized controlled trial to compare implementation and student outcomes of three training strategies: Control Condition (CC), Remote Video (RV), and Remote Video plus Coaching (RV+).

Setting/Participants:

Participants will be school personnel with and without prior mental health training and students in grades 4-8 in schools serving rural communities who are deemed at risk for externalizing and internalizing mental health disorders. The pilot trial will be conducted in 24 schools (8 in CC, 8 in RV, and 8 in RV+). It is estimated that a total of 72 behavioral health staff (3 staff per school- 24 per arm) and 312 students (13 students per school - 104 per arm) will participate in this study. Additionally, we estimate about 24 school administrators such as principals or assistant principals will approve school's participation.

Study Interventions and Measures:

This study is designed to test the effectiveness of initial training compared to remote video training and remote video training plus coaching to train BHS to implement EBPs. Each school will be randomly assigned to receive one of three training supports: (a) Initial training (CC) (b) Initial training, plus video (RV) or (c) Initial training plus video, plus remote coaching (RV+). BHS in the RV+ condition will receive consultation from a CHOP consultant regarding implementation of EBPs, whereas BHS in the RV condition will be given access to the asynchronous training video modules. Participants in all three conditions will receive treatment manuals for the interventions they have chosen. The EBPs to be implemented by the BHS include: Coping Power Program (CPP), CBT for Anxiety Treatment in Schools (CATS), and Check-in/Check-out (CI/CO). All BHS will conduct one CPP or CATS group with 5 students of similar developmental level (e.g., a group of 4th &

5th graders), and that each school staff in CI/CO will implement the intervention with 4 separate individual students of any eligible school grade.

1 BACKGROUND INFORMATION AND RATIONALE

1.1 Introduction

Eighty-four percent of Mental Health Professional Shortage Areas are located in rural and frontier areas.¹ Children and adolescents in rural settings are less likely to receive services compared to their urban and suburban counterparts and even fewer are likely to receive evidence-based care.^{2,3} Schools have become more involved in the delivery of mental health services and hold great potential for increasing access for children and adolescents. Innovations in training and service delivery are needed to improve mental health care quality and availability in rural schools.^{4,5} Evidence-based practices (EBPs) can be incorporated into school-wide multi-tiered systems that are currently being used to improve school climate and safety. School-wide Positive Behavioral Interventions and Supports (PBIS), a service-delivery strategy based on the public health model is one example.⁶⁻⁸ A growing number of schools in rural areas are employing PBIS.⁹⁻¹² Given the large service disparities for children in rural areas, offering EBPs through PBIS can improve access and lead to better long-term outcomes.¹³

PBIS is a multi-tiered framework for defining and organizing services, including mental health services. Emphasis is placed on teaching key behavioral expectations and routines to all students. Two key features of PBIS are its scalability and its compatibility with an array of mental health EBPs. Tier 1 strategies focus on preventing new cases of problem behaviors by using universal strategies such as effective instructional practices, classroom behavior management, and school-wide discipline. Tier 2 strategies focus on supporting children with, or at risk for, mental health disorders, and Tier 3 strategies offer individualized support for more severe cases. In urban schools, school-wide PBIS has been used to incorporate EBPs at Tier 2 and Tier 3.¹⁴⁻¹⁶ Previous research has demonstrated that school personnel, with or without prior mental health training, can implement Tier 2 interventions with fidelity and clinical effectiveness if given adequate consultation support.^{15,16,17,18} In urban and suburban schools, this support (training plus ongoing consultation) can be provided to school staff on site. However, providing ongoing on-site support is not feasible or sustainable in the majority of rural schools, due to their remote physical location. For this reason, video technology has been recommended for the training of behavioral health staff (BHS) in under-served rural communities.^{19,20}

1.2 Name and Description of Intervention

1.2.1 Remote Video Training Strategy Development

We will use a remote training strategy to train BHS to implement EBPs to students in schools serving rural areas. We have obtained approval from the IRB for Phase 1 of this study (protocol ID: 20-017895). The remote video training strategy was developed during Phase 1 (years 1-2) of this 5-year grant using a community-based participatory research (CBPR)^{21,22} approach to assess barriers and facilitators to participation in a remote training. We used an iterative development framework to build the training strategy. The framework, rapid prototyping, originally used for software development,^{23,24} is based on a cyclic

process of analyzing data from users in order to improve successive prototypes. Applied to the development of psychosocial interventions, prototyping involves the creation of a “low fidelity” version of the intervention that contains key functions of interest in order to test a concept and facilitate rapid evaluation and feedback.²⁵ Following the evaluation of the early prototypes, a fully functional “high fidelity” prototype is created that is more similar to the final product and that offers fully interactive content.²⁶

1.2.2 Asynchronous and Synchronous Trainings for Implementation of EBPs

Our online strategy, which will utilize WebEx video technology, will offer protected access to asynchronous training materials such as training “modules” that include didactic content, audio and visual examples, as well as treatment materials and resources, all of which can be viewed at the trainee’s individual pace and convenience. The remote training strategy will also allow synchronous training and consultation for the implementation of EBPs by school staff supported by expert consultants, and communication between consultants and school personnel to coordinate services in a child-centered approach for student participants who are already receiving other services at school.

1.2.3 Benefits of a Remote Training Strategy

Advantages of web-based remote training include flexibility, accessibility, cost-efficiency, potential for both didactic and interactive learning, and consistency in quality.^{20,27} Remote online training allows for synchronous (i.e., interactive) supervision and feedback from a supervisor anywhere in the country (or the world). This allows for the trainee to be able to receive ongoing consultation or supervision on site without the time and cost of travel.²⁷⁻²⁹

Though findings are preliminary, remote technology-enhanced programs have been found to be acceptable and feasible in community settings.^{30,31} Studies suggest that technology-based training methods, particularly when developed using the latest multimedia and interactive design formats, may be more effective than manuals alone and as effective as face-to-face training workshops in disseminating EBPs to community mental health professionals.^{20,31-33}

1.2.4 Tier 2 Interventions

CBT for Anxiety Treatment in Schools (CATS): CATS is an adaptation of Friends for Life (FRIENDS).³⁴ The adapted protocol retains the core elements of evidence-based CBT for anxiety and the FRIENDS group format. We implemented planned adaptations to the protocol based on our collective experience with the protocol, two previous implementation studies,^{17,35} and focus groups and qualitative interviews with stakeholders. We followed procedures developed by Lee and colleagues³⁶ and Bernal et al.³⁷ regarding the appropriateness of FRIENDS for the target population. We conducted qualitative interviews with five consultants and six focus groups with school counselors who used FRIENDS. We made changes to the language (idioms, metaphors, words), cultural fit (cultural values), methods (session length [40 minutes], number of sessions [8 sessions]), and activities (in-session practices), which resulted in additions and substitutions in these areas, while maintaining the 5 essential components of the treatment.^{38,39} This resulted in a briefer (8-session) and more feasible, engaging and culturally appropriate protocol for urban under-resourced schools than the original FRIENDS.

Coping Power Program (CPP): Coping Power Program is an evidence-based intervention designed for students with externalizing behavior disorders. CPP is comprised of twelve 45-minute sessions. This EBP has been shown to be effective at reducing aggressive behavior and substance abuse among aggressive boys, with gains maintained at one-year follow-up.⁴⁰ Growth curve analyses showed that CPP had linear effects for three years after intervention on reductions in aggressive behavior and academic behavior problems.⁴¹

Check-in/Check-out (CI/CO): CI/CO is a targeted, Tier 2 intervention for students at risk of developing externalizing and internalizing mental health disorders.^{42,43} CI/CO is designed to provide immediate feedback (i.e., at the end of each class period) to students, based on the use of a daily report card. This feedback is developmentally sensitive.^{42,43} CI/CO implementers meet individually with students for a brief ‘check-in’ in the morning and a brief ‘check-out’ in the afternoon. Research on the use of CI/CO has shown it to be effective in reducing externalizing and internalizing problems with elementary school students.^{43,44,45} CI/CO will be offered to individual students for a variable period of time, depending on need.

1.3 Findings from Non-Clinical and Clinical Studies

We conducted a needs assessment and resource-mapping study in Pennsylvania schools that currently implement PBIS. According to the Pennsylvania Positive Behavior Support (PaPBS) Network, 171 elementary and middle schools in Pennsylvania are currently implementing PBIS with fidelity. We asked a member of each school leadership team at 85 schools, randomly selected from the pool of 171 schools, to complete an electronic survey about their school’s PBIS program (e.g., How do the PBIS and mental health teams’ function?). Participants completed the Survey on School Readiness for Interconnecting Positive Behavior Interventions and Supports and School Mental Health.⁴⁶ We collected 48 responses (56% response rate) from PBIS Leadership Team members. Schools were classified as being located in a suburb (40%), rural area (35%), town (15%), or city (10%).⁴⁷ Compared to non-rural schools (N = 31), rural schools (N = 17) showed a significantly higher Total Readiness⁴⁸ for interconnecting PBIS with mental health ($t = 2.34, p < .05$). Scores for all rural schools were within the “ready” range for interconnecting with mental health supports.²² Also, rural schools reported having significantly more staff support for PBIS and school mental health programs, on average, compared to non-rural schools ($t = 2.49, p < .05$). Of the rural schools, all reported offering Tier 2 services, including 77% Social Skills Training, and 47% Check and Connect. None of the rural schools reported the use of manualized group-based mental health interventions or interventions for internalizing disorders. Approximately 65% of participants in rural schools reported receiving training, supervision/consultation for Tier 2; however, these implementers received initial training only (e.g., conferences, in-service professional development) with little ongoing or follow-up consultation or supervision. The study shows that rural schools have the capacity and readiness to implement Tier 2 mental health EBPs because all of them are already offering Tier 2 services. However, there is a clear need for training and consultation on manualized group and individual interventions for externalizing and internalizing mental health.

1.4 Relevant Literature and Data

1.4.1 Mental Health Services in Rural Schools

There is a pressing need to increase capacity to provide quality mental health services in rural schools. Rural areas have fewer and less well trained health care providers than non-rural areas.² Problems specific to mental health services in rural schools include staff turnover²³ and low levels of funding for mental health services.⁵⁰ Even though most rural schools have some school personnel with mental health training, the approach most schools take with regard to dealing with mental health problems is to assess and refer to an outside provider. Given the shortages of mental health providers in most rural communities, this option simply leads to children not being served. The second option taken by BHS in rural schools is to assess and treat students individually. However, given the high need for services, BHS in rural schools are not always able to see individual students for more than a brief period of time and many children in need of services never receive help.⁴⁷ There is mounting evidence that school-based mental health programs can effectively address emotional and behavioral disorders.⁵¹ A number of comprehensive school-wide prevention approaches have been found to have a positive effect on an array of behavioral, emotional and academic outcomes. One such approach is school-wide PBIS⁵², a multi-tiered framework for defining and organizing practices and interventions.⁵³ One potential innovation to increase access to services is to incorporate EBPs into PBIS.⁶⁻⁸ PBIS programs can also incorporate targeted group-based mental health EBPs for children at risk (Tier 2) and individualized EBPs for more severe cases (Tier 3). A growing number of schools in rural areas are employing PBIS at Tier 1.⁹⁻¹² However, rural schools are not able to provide Tier 2 support unless BHS are given adequate training and consultation on EBP implementation.

The problems of shortage of providers with appropriate training in EBP implementation and the common practice of assess-and-refer can be addressed via remote training of school personnel and by integrating mental health services into existing service delivery strategies. Remote video technology offers the potential to provide training and consultation for behavioral health staff in rural schools. Based on our reading of the relevant literature and our collective experience developing programs in the school setting, we propose that the development of a training approach for BHS in rural school settings ought to (a) include a training system for BHS to enhance knowledge and skill needed for implementation, (b) use remote video technologies, and (c) incorporate implementer and school context factors to increase the strategy's perceived feasibility, appropriateness and acceptability by stakeholders.

1.5 Compliance Statement

This study will be conducted in full accordance with all applicable Children's Hospital of Philadelphia Research Policies and Procedures and all applicable Federal and state laws and regulations including 45 CFR 46. 21 CFR Parts 50, 54, 56, 312, 314 and 812.

The investigators will perform the study in accordance with this protocol, will obtain consent and assent (when appropriate), and will report unanticipated problems involving risks to subjects or others in accordance with The Children's Hospital of Philadelphia IRB

Policies and Procedures and all federal requirements. Collection, recording, and reporting of data will be accurate and will ensure the privacy, health, and welfare of research subjects during and after the study.

2 STUDY OBJECTIVES

2.1 Primary Objective (or Aim)

The purpose of this study is to conduct a pilot randomized controlled trial comparing three training strategies: Control Condition (CC), Remote Video (RV), and Remote Video plus Coaching (RV+).

2.2 Secondary Objectives (or Aim)

The secondary objectives are the evaluation of implementation and student outcomes.

- To explore mediators and moderators of consultation support on behavioral health staff fidelity.
- To qualitatively examine school staff's perceived feasibility, appropriateness and acceptability of the support they received.

3 INVESTIGATIONAL PLAN

3.1 General Schema of Study Design

This study is a pilot randomized controlled trial. The three arms are: (a) Initial remote training (b) Initial remote training, plus video and (C) Initial remote training, plus video, plus remote coaching. Each school will be instructed to select CICO and one of the two group EBP protocols for use.

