3.1.1 Pre-Trial Activities and Screening Phase

The Remote Training Strategy was developed during Phase 1 of this 5-year project using an iterative process (*Rapid Prototyping*) to develop the appropriateness, feasibility, acceptability and preliminary efficacy of the online training platform.

School Selection: The National Center for Education Statistics (NCES) subdivides rural and town school areas by their proximity to an urbanized area into fringe, distant, or remote locations.⁴⁷ Participant schools will be located in any of these three rural locations or town, remote area and/or the school will serve rural communities. We will invite 24 schools representing the 2 geographic locations (urban/rural) to participate in the pilot efficacy study. After receiving school approval to participate schools will be stratified based on the geographic location and a computer-generated block randomization list will be prepared to randomize the 24 schools in a 1:1:1 ratio to either RV, RV+ or CC (8 schools/arm) stratified by geographic locations (urban/rural). The block randomization with varying will ensure ensure equal number of schools in each arm and eliminate the predictability of schools' assignment.

Behavioral Health Staff Screening: Recruitment will begin with assistance from the school principal who may nominate school behavioral health staff to participate in the study. Additionally, the research staff will reach out to school behavioral health staff concurrently with the school principal. The research staff will speak with school staff by phone or via WebEx to clearly explain study procedures, as well as potential risks and benefits. BHS will be clearly informed of the voluntary nature of their participation and will receive ample opportunities to ask questions. A copy of the consent form will be provided to the BHS, and consent will be obtained electronically via REDCap.

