3.1.2 Phase 1: Training of Behavioral Health Staff

All initial trainings will be lead by research staff and will be conducted remotely via Webex. These initial trainings will be recorded and made available to all participants to reference for the duration of their participation in the study.

Initial Red Flags and Screening Training: Research staff will train school staff from all conditions remotely on identifying “red flags” that a student is struggling with anxiety, anger, or other mood disorders and how this information can help Tier 2 Team members and teachers make informed referrals for the interventions. Study participants should use this information to hold a brief professional development with school staff to help guide their referrals. Additionally, participants will be taught about how the referral and screening

process operates, including who is responsible for each aspect of the process, how the screening measures are scored and what those scores mean. We will train BHS using strategies that have been proven effective, including the teaching of the theoretical approach used in the intervention, active demonstration and practice of skills, and coaching. ^{56,57}

Initial Evidence-Based Programs Training: Research staff will train school staff from all conditions remotely on the three EBPs. The three EBPs that schools staff will be trained on are Coping Power Program (CPP) ⁵⁸ for externalizing behavior disorders, CBT for Anxiety Treatment in Schools (CATS) ⁵⁹ for anxiety disorders, and Check-in/Check-out (CI/CO) ⁶⁰ for externalizing and internalizing ⁶¹ disorders. Three separate trainings will be held to introduce participants to the interventions and provide an overview and understanding of each EBP.

Video Training Modules: We will offer protected access to asynchronous training materials to BHS in the Remote Video and Remote video plus coaching conditions. These trainings will include “modules” that are comprised of didactic content, audio and visual examples, as well as treatment materials and resources, all of which can be viewed at the trainee’s individual pace and convenience. Participants will have access to the training modules via CHOP OPEN and they will be able to login using a unique username and password.

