4.3 Phase 2: Implementation of EBPs

We expect that each school will have one staff member with prior mental health training (e.g., school counselor). This person will be expected to implement one of the group-EBPs. The two other staff members will be tasked with implementing CI/CO, as this intervention can be implemented by school staff without prior mental health training.^{63,68} We estimate that the staff member with mental health training will conduct one CPP or CATS group with 5-6 students of similar developmental level (e.g., a group of 4th & 5th graders; 144 students

total), and the other implementers will lead CI/CO and will implement the intervention with 6 individual students of any school grade (144 students total). Following the initial live training, BHS will be instructed to conduct targeted screenings with the grade group they would like to select for participation in the study.

Research consultants will provide technical assistance to support behavioral health staff. The three EBPs that schools will use for Tier 2 are the Coping Power Program (CPP)⁵⁸ for externalizing behavior disorders, CBT for Anxiety Treatment in Schools (CATS)⁵⁹ for anxiety disorders, and Check-in/Check-out (CI/CO)⁶⁰ for externalizing⁶¹ disorders. CPP and CATS will be implemented in group format with students of similar developmental level (e.g., 4th & 5th or 7th & 8th grade together) during the lunch or free period. BHS could also use CI/CO for individual students who do not meet inclusion criteria for CPP or CATS. Each school will be instructed to select CI/CO and one of the two CBT protocols for use.

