5.3 Implementation Fidelity

Content Fidelity to Tier 2 Group CBT (CPP & CATS). The Content Fidelity Checklist (CFC) reflects each activity component of the session agenda of the treatment protocols. Raters use a yes/no response scale to indicate whether or not the implementer covered a particular component. All GCBT sessions will be audio-recorded. 100% of sessions will be

coded by the first coder and approximately 20% of sessions will be randomly selected and coded by the second coder. Interrater reliability will be evaluated using Kappa coefficients⁶⁹

Process Fidelity to Tier 2 Group CBT (CPP & CATS). Process fidelity will be assessed via an adapted version of the rating system developed by Lochman and colleagues.⁷⁰ Ten items are rated on a scale of 0 to 4, with 0 being "Not At All" and 4 being "Very Often". Ratings are given on the extent to which school staff members delivered the intervention in an orderly fashion, using active learning strategies, etc. Exploratory factor analysis (EFA) yielded two factors on the 10-item scale. We will use the average *Total* and factor scores for analysis. 100% of sessions will be coded by the first coder and approximately 20% of sessions will be coded by the second coder. Interrater reliability will be evaluated using ICC.

Content Fidelity for CI/CO. Content fidelity for CI/CO will be assessed via the CI/CO Implementation Guide Fidelity Checklist (IGFC). The CI/CO IGFC is completed by the consultant (research staff) after school teams submit their completed CI/CO Implementation Guide. The IGFC is completed once and measures both the content and quality of the customized manual components for each school. The CI/CO IGFC/Content Measure is a 26-item measure of CI/CO customization of the following CI/CO components: (a) staff roles and responsibilities, (b) CI/CO process logistics, (c) daily progress report, (d) motivation system, (e) fading and self-monitoring procedures, (f) staff training procedures, and (g) data collection and progress monitoring procedures. Each item is scored according to completion status as "yes," "no," or "not applicable." The CI/CO IGFC/Content Measure will be scored by recording the frequency of "yes" scores over the frequency of "yes," and "no" scores.

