8 STUDY ADMINISTRATION

8.1 Treatment Assignment Methods

8.1.1 Randomization

The 24 invited schools will be recruited from 2 geographic locations (urban/rural). Schools will be stratified based on the geographic location and a computer-generated block randomization list will be prepared to randomize the 24 schools in a 1:1:1 ratio to either RV, RV+ or CC (8 schools/arm) stratified by geographic locations (urban/rural). The block randomization with varying will ensure equal number of schools in each arm and eliminate the predictability of schools' assignment. It is estimated that a total of 72 behavioral health staff (3 staff per school- 24 per arm) and 312 students (13 students per school- 104 per arm) will participate in this randomized parallel groups pilot study.

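### Each school's choice of CPP or CATS is neither recorded before allocation, balanced nor adjusted for, so programme mix can differ between arms

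*Combined protocol and SAP*

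**What the plan says.** Section 3.1 states "Each school will be instructed to select CICO and one of the two group EBP protocols for use". Section 4.3, under Phase 2, repeats it: "Each school will be instructed to select CI/CO and one of the two CBT protocols for use". Neither says when the choice is made relative to allocation.

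Randomisation belongs to the pre-trial phase and is triggered by school approval: "After receiving school approval to participate schools will be stratified based on the geographic location" (section 3.1.1). Section 8.1.1 names the same single factor: "Schools will be stratified based on the geographic location and a computer-generated block randomization list will be prepared". There are 24 schools, 8 per arm.

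Section 3.1.2 adds "Research staff will train school staff from all conditions remotely on the three EBPs", so no school has to choose before training. Section 4.2.2 opens the videos after initial training and student identification, and describes the programmes at that stage as those staff intend to use.

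On analysis, the section 6.3 model has arm, time and their interaction. Section 6.2 adds a covariate only when a baseline outcome differs significantly between groups. The Adoption Inventory (section 5.3) records programme use per school and condition, but no analysis is assigned to it. Moderators of fidelity are planned (sections 2.2 and 6.3) but none is named.

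**The concern.** The group programme is a strong school-level factor. CATS targets anxiety in 8 sessions; CPP targets externalizing behavior in 12 (section 1.2.4). The Content Fidelity Checklist "reflects each activity component of the session agenda of the treatment protocols" (section 5.3), so its items differ by programme. BASC-3 Aggression, Conduct Problems and Anxiety are all primary student endpoints (section 6.1), and the two programmes do not aim at the same ones. Choice can also affect which students enter, because the SAEBRS Social Behavior subscale sets eligibility for CPP and CI/CO (section 5.1), while the SCARED screens for anxiety.

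If the mix differs between arms, a contrast meant to isolate the training strategy partly compares CPP with CATS. For fidelity, it also partly compares two checklists. The pilot exists to estimate effect sizes (section 6.4) and to supply estimates for a larger trial (section 6.3), so a distorted contrast would carry forward.

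**Working it through.** **1. The plan's own margins (section 6.4).** Half-width = t(0.975, 2n-2) x SD x sqrt(2/n).
- Content fidelity, n = 24, SD 16: 2.013 x 16 x sqrt(2/24) = 9.30 (stated 9.3).
- Process fidelity, n = 24, SD 0.6: 2.013 x 0.6 x sqrt(2/24) = 0.349 (stated 0.35).
- Student change, n = 89, SD 8: 1.974 x 8 x sqrt(2/89) = 2.37 (stated 2.4).

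All three reproduce. None allows for clustering by school.

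**2. Who the choice affects.** One of three staff per school runs the group (sections 3.2.1 and 4.3), so 8 per arm. By the abstract, 5 of 13 students per school are in the group. Sections 3.2.1 and 4.3 instead give 144 group and 144 CI/CO students, which is half and does not add to 312. Both shares are carried below.

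**3. Chance imbalance if choice is independent of arm.** With K of 24 schools choosing CPP and arms of 8, ignoring the geographic strata:

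P(a, b, c) = C(8,a) C(8,b) C(8,c) / C(24,K), where a + b + c = K.

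| K (assumed) | A given pair differs by 3 or more | RV or RV+ differs from CC by 3 or more |
|---|---|---|
| 8 | 0.193 | 0.333 |
| 12 | 0.220 | 0.345 |
| 16 | 0.193 | 0.333 |

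Values of K between these give 0.19-0.22 and 0.32-0.37. The last column is the relevant one, since section 6.4 plans RV or RV+ against CC. If choice responds to arm, these probabilities do not bound the difference.

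**4. Shift in a contrast.** Shift = difference in CPP share x CPP-CATS outcome difference D x share of units in the group programme. D is not in the documents, so it is assumed over a range. A 3-school imbalance is a share difference of 3/8.

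*Content fidelity, D = 4 to 16 points*
- Group implementers: 3/8 x 4 = 1.5, to 3/8 x 16 = 6.0. The matching half-width at n = 8 is 2.145 x 16 x sqrt(2/8) = 17.2.
- All staff (one third in groups): 0.5 to 2.0, against 9.3.

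*Student change, D = 2 to 8 points*
- Group students: 0.75 to 3.0. With 5 x 8 = 40 per arm and 15% attrition, n = 34 and the half-width is 1.997 x 8 x sqrt(2/34) = 3.9.
- All students: 0.3 to 1.2 with a 5/13 share, or 0.4 to 1.5 with one half, against 2.4.

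**The case against.** **Chance imbalance is not bias.** If choice is independent of arm, a difference in mix is ordinary variation in a school-level factor, and many such factors can differ with 8 schools per arm. This stands where the standard error is at school level. Section 6.3 only explores school-level clustering, and its listed t-tests and student-level model would not reflect that variation.

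**Choice that responds to arm may be part of the strategy's effect.** The aim is to compare training strategies by intention to treat, so a shift in programme is arguably one of their consequences. This largely stands for student outcomes. It is weaker for content fidelity, where the measure itself changes with the programme. It also means that adjusting for the programme delivered would condition on a post-randomisation variable and could introduce bias.

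**The documents do not show that schools choose knowing their arm.** A reader might infer this from the abstract, where manuals follow the chosen interventions, or from section 4.2.2. The abstract describes equal provision in all three conditions, and section 4.2.2 is compatible with late choice without dating it. Nor does anything say that one programme is easier or scores lower.

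**Early commitment has a cost.** Screening follows initial training (section 4.3), so a binding choice would precede knowledge of whether eligible students are mainly anxious or externalizing. Crossing programme with geography gives four strata averaging six schools for three arms. Both points stand, and they argue for a non-binding declaration and against requiring stratification.

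**The analysis is still open.** Section 6 allows the SAP to be updated before database lock. That covers a model term, but a pre-allocation declaration cannot be obtained once schools know their arm.

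**Conclusion.** The point holds as a gap that permits imbalance, and as a cheap improvement worth making. No rule dates the choice, no stratum balances it, and no model term accounts for it. An imbalance of 3 or more schools between at least one active arm and control would arise by chance in about a third of trials, assuming 8, 12 or 16 CPP schools and choice independent of arm.

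The consequence is modest. A 3-school imbalance is worth at most 6.0 points against a half-width of about 17.2 among group implementers, or 2.0 against 9.3 over all staff, at the top of the assumed 4-16 point range. Student contrasts over everyone enrolled are diluted in the same way, because only 5 of 13 students (half, on the section 3.2.1 figures) are in a group.

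Two stronger readings are not supported. One is that the arm contrasts are biased: that requires choice to depend on arm, which the documents allow but do not state. The other sets a group-implementer shift against the all-staff margin. With an assumed 10-point difference, 10 x 3/8 = 3.75 looks like 40% of 9.3, but the denominators differ. On matching bases it is 3.75/17.2 = 22%, or 1.25/9.3 = 13%.

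**What to change.** 1. Record each school's intended group programme on the enrolment form before its allocation is released. The declaration need not bind the school.
2. Include that declaration, not the programme finally delivered, as a school-level fixed effect in the fidelity and student models. In the pre/post repeated-measures model, enter it with its interaction with time; a main effect alone shifts both time points equally and leaves the arm-by-time contrast essentially unadjusted.
3. Report group fidelity and student outcomes by programme delivered (CPP, CATS, CI/CO), by arm, as a descriptive supplement. This also shows any switching after allocation, which the adjustment does not remove.
4. Treat stratification on programme as optional, given four small strata among 24 schools.

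The cost is one form field and about one of the 24 - 3 = 21 school-level degrees of freedom. The declared programme may also differ from the one delivered after screening, which weakens the adjustment. Step 1 has to be in place before schools are allocated; steps 2 and 3 can go into the SAP update before database lock.
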